3.2.3 Toxicology

Animal studies

A 2-year carcinogenicity study was conducted in B6C3F1 mice at doses of 3, 35, 250, and 500 mg/kg/day for males and 3, 35, and 250 mg/kg/day for females; an increased incidence of benign hepatocellular adenomas was noted at 250 mg/kg/day (290-fold the MRHD of a 0.5-mg daily dose) in female mice only. Two of the 3 major human metabolites have been detected in mice. The exposure to these metabolites in mice is either lower than in humans or is not known. Dutasteride was tested for genotoxicity in a bacterial mutagenesis assay (Ames test), a chromosomal aberration assay in CHO cells and a micronucleus assay in rats. The results did not indicate any genotoxic potential of the parent drug. Two major human metabolites were also negative in either the Ames test or an abbreviated Ames test.

Treatment of sexually mature male rats with dutasteride at 0.1-to 110-fold the MRHD (animal doses of 0.05, 10, 50, and 500 mg/kg/day for up to 31 weeks) resulted in dose- and time-dependent decreases in fertility; reduced cauda epididymal (absolute) 17 sperm counts but not sperm concentration (at 50 and 500 mg/kg/day); reduced weights of the epididymis, prostate, and seminal vesicles; and microscopic changes in the male reproductive organs. The fertility effects were reversed by recovery week 6 at all doses, and sperm counts were normal at the end of a 14-week recovery period.

3.2.4 Adverse Events

Adverse Events with Possible Relationship to Dutasteride		
Likely (>20%)	Less Likely (≤20%)	Rare but Serious (<3%)
	Impotence	Angioedema
	Libido decreased	Cardiac failure,
	Ejaculation disorders	Depressed mood
	Gynecomastia (including breast tenderness, and breast enlargement)	Dizziness
		Localized hypersensitivity
		Pruritus, rash, skin reactions
		Urticaria
		TSH increased

3.2.5 Pregnancy

Pregnancy Category X. Dutasteride is contraindicated for use in women of childbearing potential and during pregnancy. Sexually active men with partners in child bearing age group are recommended contraceptive use when taking this medication.

3.3 Finasteride

3.3.1 Description:

General: Finasteride is 4-azaandrost-1-ene-17-carboxamide, N-(1,1-dimethylethyl)-3-oxo-, (5 α ,17 β)-. Finasteride is a white crystalline powder with a melting point near 250°C. It is freely soluble in chloroform and in lower alcohol solvents, but is practically insoluble in water

Molecular weight of 372.55.

Molecular formula: C₂₃H₃₆N₂O₂

3.3.2 Pharmacology

Mechanism of action: Finasteride is a competitive and specific inhibitor of Type II 5 α -reductase with which it slowly forms a stable enzyme complex. Turnover from this

complex is extremely slow ($t_{1/2} \sim 30$ days). This has been demonstrated both *in vivo* and *in vitro*. Type II 5 α -reductase metabolizes testosterone to DHT in the prostate gland, liver and skin. DHT induces androgenic effects by binding to androgen receptors in the cell nuclei of these organs.

Pharmacokinetics: The mean bioavailability of finasteride 5-mg tablets was 63% (range 34-108%), based on the ratio of area under the curve (AUC) relative to an intravenous (IV) reference dose. Maximum finasteride plasma concentration averaged 37 ng/mL (range, 27-49 ng/mL) and was reached 1-2 hours postdose. Bioavailability of finasteride was not affected by food. Mean steady-state volume of distribution was 76 liters (range, 44-96 liters). Approximately 90% of circulating finasteride is bound to plasma proteins. There is a slow accumulation phase for finasteride after multiple dosing.

Finasteride is extensively metabolized in the liver, primarily via the cytochrome P450 3A4 enzyme subfamily. Two metabolites, the t-butyl side chain monohydroxylated and monocarboxylic acid 10 metabolites, have been identified that possess no more than 20% of the 5 α -reductase inhibitory activity of finasteride. In healthy young subjects (n=15), mean plasma clearance of finasteride was 165 mL/min (range, 70-279 mL/min) and mean elimination half-life in plasma was 6 hours (range, 3-16 hours). Following an oral dose of 14C-finasteride in man (n=6), a mean of 39% (range, 32-46%) of the dose was excreted in the urine in the form of metabolites; 57% (range, 51-64%) was excreted in the feces.

The mean terminal half-life of finasteride in subjects ≥ 70 years of age was approximately 8 hours (range, 6-15 hours; n=12), compared with 6 hours (range, 4-12 hours; n=12) in subjects 45-60 years of age. As a result, mean AUC(0-24 hr) after 17 days of dosing was 15% higher in subjects ≥ 70 years of age than in subjects 45-60 years of age ($p=0.02$).

3.3.3 Toxicology

Animal studies

No evidence of a tumorigenic effect was observed in a 24-month study in Sprague-Dawley rats receiving doses of finasteride up to 160 mg/kg/day in males and 320 mg/kg/day in females. These doses produced respective systemic exposure in rats of 111 and 274 times those observed in man receiving the recommended human dose of 5 mg/day. All exposure calculations were based on calculated AUC(0-24 hr) for animals and mean AUC(0-24 hr) for man (0.4 μ g•hr/mL).

No evidence of mutagenicity was observed in an *in vitro* bacterial mutagenesis assay, a mammalian cell mutagenesis assay, or in an *in vitro* alkaline elution assay. In an *in vitro*

chromosome aberration assay, using Chinese hamster ovary cells, there was a slight increase in chromosome aberrations. These concentrations correspond to 4000-5000 times the peak plasma levels in man given a total dose of 5 mg. In an *in vivo* chromosome aberration assay in mice, no treatment-related increase in chromosome aberration was observed with finasteride at the maximum tolerated dose of 250 mg/kg/day (228 times the human exposure) as determined in the carcinogenicity studies. In sexually mature male rabbits treated with finasteride at 543 times the human exposure (80 mg/kg/day) for up to 12 weeks, no effect on fertility, sperm count, or ejaculate volume was seen.

3.3.4 Adverse Events

Adverse Events with Possible Relationship to Finasteride		
Likely (>20%)	Less Likely (≤20%)	Rare but Serious (<3%)
	Orthostatic hypotension	Angioedema
	Dizziness	Cardiac failure,
	Ejaculation disorders	Depressed mood
	Decreased libido	Altered mental status
	Gynecomastia (including breast tenderness, and breast enlargement)	Localized hypersensitivity
		Pruritus, rash, skin reactions
		Urticaria

3.3.5 Pregnancy

Pregnancy Category X. Finasteride is contraindicated for use in women of childbearing potential and during pregnancy. Sexually active men with partners in child bearing age group are recommended contraceptive use when taking this medication.

3.4 Blood Donation

Men being treated with study drugs should not donate blood until at least 6 months have passed following their last dose. The purpose of this deferred period is to prevent administration of study drug to a pregnant female transfusion recipient, for which this drug is not safe.

3.5 Selection of Doses Used in the Study

The recommended dose of enzalutamide is 160 mg/day based on the data from several trials. The durability of disease suppression was similar between the 150 mg/day and the 240 mg/day dose cohorts in post-chemotherapy patients in the Phase 1-2 study.(59) Given this comparable efficacy, with dose-dependent increases of Grade 3 fatigue (0% at 150 mg/day vs. 9% at 240 mg/day), and reports of seizure at high doses (one witnessed event at 360 mg/day and another at 600 mg/day), a dose of 160 mg/day was believed to have the optimal risk/benefit profile and was selected for investigation in a phase 3 randomized double blind trial (AFFIRM). (21) The results of this trial indicated efficacy with good tolerance, therefore based on all the above data, we plan to use the recommended dose of enzalutamide 160 mg/day for the current trial.

The recommended dose of dutasteride is 0.5 mg/day. The current dose is selected based upon the results of a placebo controlled phase III study in patients with benign prostate hypertrophy in which dutasteride 0.5 mg administered once daily.(60) This dose was well tolerated by patients in the study, including those in the older population.

The recommended dose of finasteride is 5mg/day. The current dose is selected based upon the results of placebo controlled study(PLESS) in which finasteride 5mg was administered once daily.(61) Similar dosage was also evaluated in combination with first generation antiandrogens and was noted to be well tolerated and efficacious.(16)

4.0 STAGING CRITERIA

The AJCC Seventh Edition, 2010 will be used in evaluating patients by the treating investigators for staging purposes.

5.0 SELECTION OF STUDY POPULATION

5.1 Eligibility Criteria

The study population will include men aged 65 years and older with hormonally naïve, progressive, systemic PCa (either biochemical recurrence with a PSA doubling time of ≤ 9 months or hormonal naïve metastatic disease confirmed by imaging) who are not candidates for treatment with ADT because the anticipated risk of ADT may outweigh the potential benefits **as determined by the treating physician**. The treating physician will determine whether the patient would have a high risk of side effects from standard ADT. **This eligibility criteria has been incorporated previously in other clinical trials focused on cancer treatment in the elderly, such as the FOCUS-2 trial** which used this eligibility to enroll older patients with advanced colorectal cancer for dose-modified chemotherapy.(58) Physicians in the FOCUS2 trial deemed the patient "not fit" for

standard of care therapy as part of the eligibility criteria for enrollment. In the current trial case report forms (CRF) will be record details as to why each patient was considered for the trial and not ADT.

Each of the criteria in the following section must be met in order for a patient to be considered eligible for registration.

5.2 Inclusion Criteria

Patients must meet the following inclusion criteria:

5.2.1 Disease Related Criteria

1. Histologically or cytologically confirmed adenocarcinoma of the prostate without neuroendocrine differentiation or small cell features.
2. Patients with systemic PCa as defined by either a) hormonal naïve metastatic PCa with radiographic evidence of visceral or osseous metastasis or b) biochemical recurrence PCa that fulfills **all** of the following criteria:
 - A minimum of three rising PSA levels with an interval of \geq 1 week between each test.
 - The PSA value at the screening visit should be \geq 2 ng/ml.
 - PSA doubling time \leq 9 months.
3. Patients should be 65 years or older.
4. Patients who are deemed “not fit” by CGA or at high risk for side effects from ADT as determined by the treating physician. **A case report form will be used to document the specifics of why each eligible patient is not considered an ideal candidate for ADT.**
5. Serum testosterone level > 1.7 nmol/L (50 ng/dL) at the screening visit (non-castrate)

5.2.2 Prior Therapy Related Criteria

6. Patients could have received hormonal therapy, (ADT), as part of definitive treatment for previous localized PCa. However, they should be off any hormonal therapy for greater than six months prior to entry to clinical trial.

5.2.3 Clinical Criteria

7. ECOG performance status of 0 to 2.
8. Able to swallow the study drug and comply with study requirements.

5.3 Exclusion Criteria

Patients must **NOT** meet any of the following exclusion criteria:

5.3.1 Disease Related Criteria

1. Severe concurrent disease or infection that, in the judgment of the investigator, would make the patient inappropriate for enrollment.
2. Known brain metastases. Brain imaging studies are not required for eligibility if the patient has no neurologic signs or symptoms suggestive of brain metastasis. However, if brain imaging studies are performed, they must be negative for disease.
3. Patient is receiving treatment for another active malignancy excluding localized cutaneous squamous or basal cell carcinoma.

5.3.2 Prior Therapy Related Criteria

4. Prior treatment for systemic prostate cancer with the exception of single agent first generation non-steroidal anti androgen(bicalutamide, flutamide and nilutamide), which they could have taken for up to 2 weeks prior to the start of investigational combination. A washout period is not required.
5. Prior treatment with enzalutamide
6. Treatment with ADT, ketoconazole, abiraterone, 5-AR inhibitors (finasteride, dutasteride), estrogens, or chemotherapy in an adjuvant setting within 6 months of enrollment (Day 1 visit) or plans to initiate treatment with any of these treatments.
7. Treatment with therapeutic immunizations for prostate cancer (e.g., PROVENGE®) or plans to initiate treatment with any of these treatments during the study period.
8. Use of herbal products that may decrease PSA levels (e.g., saw palmetto) or systemic corticosteroids greater than the equivalent of 10 mg of prednisone/prednisolone per day within 4 weeks of enrollment (Day 1 visit) or plans to initiate treatment with any of these treatments during the study.
9. Radiation therapy within 3 weeks (if single fraction of radiotherapy within 2 weeks) and radioisotope therapy within 8 weeks of enrollment (Day 1 visit).
10. Participation in a previous clinical trial of an investigational agent that blocks androgen synthesis within six months.
11. Participation in a previous clinical trial of enzalutamide.
12. Use of an investigational agent within 4 weeks of enrollment (Day 1 visit) or plans to initiate treatment with an investigational agent during the study.
13. Concomitant use of strong or moderate CYP2C8 or CYP3A4 inhibitors or inducers for subjects receiving dutasteride as the 5ARI (see Appendix F)

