7.2.1 Prohibited Medications

The following medications are prohibited within 4 weeks prior to the start of study drug treatment and are prohibited during the course of the study:

- Chemotherapeutic, immunotherapeutic and biologic agents
- Systemic glucocorticoids greater than the equivalent of 10 mg per day of prednisone/prednisolone (unless needed for stress steroids or to treat presumed adrenal insufficiency)
- Estrogens
- Herbal medications that may affect PSA levels (i.e., saw palmetto)
- Androgens (testosterone, dihydroepiandrosterone [DHEA], etc.).

Use of bisphosphates or rank-ligand inhibitor is allowed but doses should be documented during the study period.

The use of strong or moderate CYP2C8 or CYP3A4 inducers or inhibitors (see Appendix F) is prohibited while on study for patients receiving dutasteride.

Patients on therapies known to be weak inhibitors/inducers or narrow-therapeutic-index substrates of CYP2C8 or CYP3A4 should be evaluated for clinically significant drug interactions, but may participate in the study with appropriate monitoring and management.

Deviation from the above guidelines should occur only if absolutely necessary for the well-being of the patient. Any deviations to the medication/treatment guidelines are to be recorded.

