7.2.2 Permitted Medications

Patients are allowed to take prescription medications as long as they are not considered to interact with the study drug as listed in the prohibited medication list. All prescription medications should be reported to the study personnel. Patients concomitantly using warfarin will need to have their INR monitored closely.

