16.6 Appendix F: Prohibited Concomitant Medications

Attached to the protocol

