APPENDIX F. Strong and Moderate CYP2C8 and CYP 3A4 Inducers and Inhibitors

NOTE: This list may not be comprehensive – review each patient's medications prior to enrollment and at every clinic visit.

CYP2C8 Strong & Moderate INDUCERS	CYP2C8 Strong & Moderate INHIBITORS	CYP3A4 Strong & Moderate INDUCERS	CYP3A4 Strong & Moderate INHIBITORS ^{oo}
Carbamazepine Phenobarbital Phenytoin Primidone Rifampin	Efavirenz Gemfibrozil Montelukast Pioglitazone Trimethoprim	Carbamazepine Efavirenz Phenobarbital Phenytoin Primidone Rifabutin	Aprepitant Atazanavir Clarithromycin Conivaptan Darunavir Diltiazem

		Rifampin St. John's Wort	Erythromycin Fluconazole Fosamprenavir Grapefruit Juice Indinavir Itraconazole Ketoconazole Nefazodone Nelfinavir Posaconazole Ritonavir Saquinavir Telithromycin Verapamil Voriconazole
--	--	-----------------------------	--

ⁱ CYP3A4 Strong & Moderate Inhibitors applies to dutasteride/enzalutamide combination therapy only, and not finasteride / enzalutamide combination therapy

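### The main text ties all strong or moderate CYP2C8 and CYP3A4 restrictions to dutasteride, while the Appendix F footnote exempts finasteride patients from CYP3A4 inhibitors only

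*Combined protocol and SAP*

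**What the plan says.** Four places in the combined protocol and SAP bear on these drugs.

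- Section 5.3.2, exclusion 13, excludes "Concomitant use of strong or moderate CYP2C8 or CYP3A4 inhibitors or inducers for subjects receiving dutasteride as the 5ARI (see Appendix F"). It covers four classes: inhibitors and inducers of each enzyme.
- Section 7.2.1 takes the same four classes and says their use "is prohibited while on study for patients receiving dutasteride". A separate sentence, with no limit by 5-AR inhibitor, deals with milder agents: "Patients on therapies known to be weak inhibitors/inducers or narrow-therapeutic-index substrates of CYP2C8 or CYP3A4 should be evaluated" for significant interactions, and may take part with monitoring.
- Section 7.2.2 lets all patients take prescription drugs "as long as they are not considered to interact with the study drug as listed in the prohibited medication list".
- Appendix F tabulates the agents in four columns. Its own heading is neutral ("Strong and Moderate CYP2C8 and CYP 3A4 Inducers and Inhibitors"); the appendix index calls it "Appendix F: Prohibited Concomitant Medications". Its footnote reads "CYP3A4 Strong & Moderate Inhibitors applies to dutasteride/enzalutamide combination therapy only, and not finasteride / enzalutamide combination therapy". It also asks sites to review each patient's "medications prior to enrollment and at every clinic visit".

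Every patient receives enzalutamide. Under Section 7.1 the choice between dutasteride and finasteride depends on insurance approval, with dutasteride preferred.

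**The concern.** For a finasteride patient, the main text and the appendix point in different directions on three of the four classes. A site working from exclusion 13 could enrol a finasteride patient who takes gemfibrozil. A site that takes the appendix footnote at its word could refuse the same man. With two recruiting sites, that could mean different eligibility decisions. Section 7.2.1 requires deviations from its medication rules to be recorded, and whether one has occurred would depend on which text is followed.

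The main text also makes an enzalutamide-relevant restriction depend on the partner drug. Two men on the same enzalutamide dose and the same CYP2C8 inhibitor would be handled differently because of their insurance. Enzalutamide exposure is not a trivial matter in this protocol: Section 3.5 reports Grade 3 fatigue of 0% at 150 mg/day against 9% at 240 mg/day, and seizures at 360 and 600 mg/day.

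**Working it through.** No published figure needs reproducing. The check sets the texts side by side, counts the agents concerned, and compares the rules with the protocol's pharmacology.

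**1. Rule by class (strong or moderate agents)**

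| Class | Entries in Appendix F | Dutasteride patient, both texts | Finasteride patient, exclusion 13 and 7.2.1 | Finasteride patient, Appendix F footnote |
|---|---|---|---|---|
| CYP2C8 inducers | 5 | barred | not restricted | barred by implication |
| CYP2C8 inhibitors | 5 | barred | not restricted | barred by implication |
| CYP3A4 inducers | 8 | barred | not restricted | barred by implication |
| CYP3A4 inhibitors | 21 | barred | not restricted | exempt |

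The texts agree for dutasteride patients throughout, and for finasteride patients on one class of four. The last column is an inference: a footnote limiting one column to dutasteride would serve no purpose if the whole table were already limited to dutasteride.

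**2. Agents concerned**

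- Entries in the first three columns: 5 + 5 + 8 = 18.
- Listed twice among them: carbamazepine, phenobarbital, phenytoin, primidone, rifampin and efavirenz, so 6.
- Distinct agents: 18 − 6 = 12. None also appears among the 21 CYP3A4 inhibitors, so the table holds 12 + 21 = 33 distinct agents.
- Split of the 12: 4 listed only as CYP2C8 inhibitors (gemfibrozil, montelukast, pioglitazone, trimethoprim); 6 listed under CYP2C8 and as CYP3A4 inducers; 2 listed only as CYP3A4 inducers (rifabutin, St. John's Wort). 4 + 6 + 2 = 12.

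**3. Fit with the protocol's pharmacology**

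- Enzalutamide (Section 3.1.2): metabolized by CYP2C8 and CYP3A4.
- Dutasteride (Section 3.2.2): CYP3A4 and CYP3A5; no CYP2C8 role is mentioned.
- Finasteride (Section 3.3.2): mainly CYP3A4.

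For CYP2C8, the only study drug with a stated role is the one everybody takes, yet the restriction is conditional on dutasteride. For the 4 agents listed only as CYP2C8 inhibitors, the protocol gives no dutasteride-related reason. For CYP3A4 the case is weaker. All three drugs are described as substrates, and both texts exempt finasteride patients from CYP3A4 inhibitors, so substrate status alone does not decide the rule for inducers.

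**4. Gap within Section 7.2.1**

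A weak CYP2C8 or CYP3A4 agent calls for an interaction check in every patient. A strong or moderate one taken with finasteride has no stated rule in that section.

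**The case against.** The strongest reply is that the operative rules do not conflict. Exclusion 13 and Section 7.2.1 contain the only sentences that prohibit these agents, they agree with each other, and by default they allow the agents with finasteride. Appendix F is a reference list without a prohibiting sentence. Its footnote remains true under the main text; it is merely redundant and may be a drafting leftover. A reader might infer that the protocol leaves finasteride patients with no rule at all, or that Section 7.2.2 could equally mean either list. The documents do not support that. The natural referent of Section 7.2.2 is Section 7.2.1, which comes directly before it and is headed as the list of prohibited medications. This part of the reply stands, and it is why the Appendix F side is stated here as an implication.

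A second reply is that the 5-AR inhibitors do differ: Section 1.3 gives dutasteride a half-life of 5 weeks against 5-6 hours for finasteride. That might motivate a CYP3A4 rule specific to dutasteride, although the protocol does not say so. It does not explain the CYP2C8 restriction.

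Third, safeguards apply to everyone: medication review, recording of concomitant drugs (Section 7.2), toxicity assessment with enzalutamide reduction to 120 or 80 mg (Section 12.0), and exclusion 14, which may already remove many users of the antiseizure drugs on the list. These limit the consequence, but none says whether the 12 agents are allowed with finasteride.

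Finally, the counts are tallies of printed examples, not measures of impact. Appendix F says its list may be incomplete, and ketoconazole, one of the 21 CYP3A4 inhibitors, may be barred separately by exclusion 6. Both caveats stand.

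**Conclusion.** The inconsistency is real and minor. Following the main text as written lets a finasteride patient take a strong CYP2C8 inhibitor, or an inducer of CYP2C8 or CYP3A4, with full-dose enzalutamide, while the Appendix F footnote implies otherwise. The CYP2C8 restriction is attached to the wrong drug on the protocol's own account of metabolism.

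Its size in printed terms is three classes of four and 12 listed agents. Its size in patients is unknown and may be zero, because the documents give neither the share expected to receive finasteride nor the use of these drugs. Sample size, power and the primary analysis are unaffected. The conclusion assumes that the footnote was meant to have a function.

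Two stronger inferences are not supported. A reader might conclude that finasteride patients would be overexposed to enzalutamide. The documents quantify no CYP interaction, and Section 3.1.2 says CYP2C8 mainly forms an active metabolite with similar activity in vitro, so the net effect of inhibiting it cannot be derived. A reader might also want a new interaction check for strong or moderate CYP3A4 inhibitors taken with finasteride. Neither the main text nor the footnote restricts them, so that duty would go beyond this defect.

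**What to change.** Amend exclusion 13 and Section 7.2.1 to match Appendix F:

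- strong or moderate CYP2C8 inhibitors, CYP2C8 inducers and CYP3A4 inducers are prohibited for all patients;
- strong or moderate CYP3A4 inhibitors are prohibited for dutasteride patients only.

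State the same rule as a sentence in Appendix F, and have Section 7.2.2 cite Appendix F by name. If the sponsor can justify a different rule, it should appear identically in all four places.

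The cost is a wording amendment. Slightly fewer finasteride patients would be eligible, or some would have to change a concomitant drug. Endpoint, sample size and analysis stay as they are.
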